3.0 Inclusion Criteria

- 3.1 Signed informed consent.
- 3.2 Patients of either gender, aged ≥18 years.
- 3.3 Karnofsky status ≥60.
- 3.4 Life expectancy of at least 12 weeks.
- 3.5 Histologically and/or clinically confirmed and/or suspicious of NET.
- 3.6 A diagnostic CT or MRI of the tumour region or suspected area within the previous 4-6 months prior to dosing day is available.
- 3.7 Recent Blood test results up to 4-6 weeks as follows:
 - 3.7.1 WBC: >2*109/L
 - 3.7.2 Haemoglobin: >8.0g/DI
 - 3.7.3 Platelets: >50x10⁹/L
 - 3.87.4 ALT, AST, AP: ≤5 times ULN
 - 3.7.5 Bilirubin: ≤3 times ULN
- 3.8 Serum creatinine: within normal range or <120µmol/L for patients aged 60 years or older.
- 3.9 Negative pregnancy test in women capable of child-bearing.

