5.0 Study design

This is a prospective, Phase 2, single center study in a total of 40 subjects with Neuroendocrine Tumors (NETs). Study participants will receive 68Ga-DOTATOC and undergo a PET/CT imaging study, to investigate its suitability as a PET imaging agent for NETs. The radiation (imaging) dose will be $111-185 \, \text{MBq} (3 - 5 \, \text{mCi}) \pm 25\%$. All doses after labeling will be presented in buffered solution for intravenous injection. Imaging will start 90 $\pm 30 \, \text{minutes}$ after injection.

About 40 patients with histologically and/or clinically confirmed and/or suspected NET are anticipated to be enrolled during 3 years from initiating the study.

Patients will be recruited at Montefiore Medical Park where there is a medical group specialised in the diagnosis and treatment of NETs. Each patient will undergo a screening visit within 14 days prior to receiving study medication.

The primary goal of the analysis is to estimate the diagnostic accuracy of 68Ga-DOTATOC PET-CT for detecting NET compared to conventional imaging techniques.

The patients will be followed up by a telephone call 24 hour after administration of test drug (⁶⁸Ga-DOTATOC) to assess if patients have experienced any adverse event. This information will be captured in the CRF for further assessment.

5.1 Image Acquisition:

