5.2. Interpretation of Data

The number of lesions that could be identified clearly as single focus will be determined for each patient. To enable a methodic and consistent approach to lesion identification, we will create 3 categories of lesion sites: organs (Head and Neck, lungs, breast, liver, pancreas, gastrointestinal tract, kidney, spleen, and pelvis/ovaries), nodal regions (Axillary, thoracic, mesenteric, abdominal, and pelvic [excluding mesenteric], and inguinal regions), and musculoskeletal system (vertebrae, bony thorax, bony pelvis, and limb bones). Because of confluence and inability to clearly delineate single liver lesions in some cases, liver metastases will be classified as 1 organ metastasis, independent of the number of liver metastases present. Lymph nodes smaller than 1 cm on CT or MRI and showing marked avidity for ⁶⁸Ga-DOTATOC will be labeled as positive for

disease. In cases where images from ¹¹¹In-Octreotide are available for comparison, the same imaging parameters will be applied. The presence of lesions will be confirmed by cross-sectional imaging of all patients with CT or MRI. As there may be lesion/s that can show abnormal focal activity on Ga-68 PET images but not on morphologic images, such lesion/s will be considered positive NET.

Each scan (⁶⁸Ga-DOTATOC) will be read by two independent, board certified nuclear medicine physicians blinded to the results of other scan. A third independent nuclear medicine physician will then review both the results (independent reviews) and clinical information to reach to a consensus.

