5.4 Statistical Analysis

The primary goal of the analysis is to estimate the diagnostic accuracy of 68Ga-DOTATOC PET-CT for detecting NET compared to conventional imaging techniques. Analyses will be performed with both patient and lesion as the unit of observation. Since all patients are expected to have at least one NET lesion, only sensitivity can be estimated in the analysis by patient, whereas both sensitivity and specificity will be estimated in the lesion based analysis. We will compute the relevant proportions and corresponding 95% confidence intervals, with adjustment for correlated data from the same patient. Results from pathology reports available from previous biopsy or surgical specimens will be considered the gold standard. In the absence of pathology reports, initial and follow up diagnostic CT or MRI scan following nonsurgical therapy including chemotherapy will be considered the gold standard.

Kappa statistics will be computed and McNemar's test will be performed to compare the sensitivity and specificity between ⁶⁸Ga-DOTATOC PET-CT with SPECT and diagnostic CT for detecting NET. All analyses will be performed in SAS and p-values < 0.05 will be considered statistically significant.

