5.4 Justification of Sample Size

We project that it will be feasible to recruit a total of 40 patients with histologically and/or clinically confirmed and/or suspected NET into the study. Each subject is expected to have on average 2 lesions and among the 80 total lesions; we project that 60% will be positive for NET. To evaluate the adequacy of the sample size (i.e., number of lesions), we computed the precision, as measured by the width of the 95% CI, with which the sensitivity and specificity of 68Ga-DOTATOC PET-CT scan can be estimated. The width of the 95% CI will be no greater than +/-14% for sensitivity and +/- 17% for specificity in the lesion-based analysis. For the patient-based analysis, the precision with which sensitivity can be estimated is +/- 15%.

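### Section 5.4 defines no reference standard for patients without earlier pathology who are untreated, or whose tissue is first obtained after the study PET

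*Combined protocol and SAP*

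**What the plan says.** Inclusion criterion 3.5 reads "Histologically and/or clinically confirmed and/or suspicious of NET", so histology is not required. The sample-size section describes the same mix, "a total of 40 patients with histologically and/or clinically confirmed and/or suspected NET into the study", and gives no share with histology.

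Section 5.4 (Statistical Analysis) sets two tiers of truth:
- Tier 1: "Results from pathology reports available from previous biopsy or surgical specimens will be considered the gold standard".
- Tier 2, when there are no pathology reports: "initial and follow up diagnostic CT or MRI scan following nonsurgical therapy including chemotherapy will be considered the gold standard".

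The same section expects every patient to have at least one NET lesion, and therefore estimates only sensitivity at patient level.

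Other relevant text:
- Criterion 3.6 requires baseline imaging: "A diagnostic CT or MRI of the tumour region or suspected area within the previous 4-6 months prior to dosing day is available".
- Section 5.1.3 compares PET foci with prior CT or MRI within 12 weeks.
- Section 5.2 states "The presence of lesions will be confirmed by cross-sectional imaging of all patients with CT or MRI", without a date. It also says of foci seen on PET but not on morphologic images that "such lesion/s will be considered positive NET".
- The only scheduled follow-up, in 5.0, is for adverse events: "The patients will be followed up by a telephone call 24 hour after administration of test drug".

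**The concern.** The primary objective is diagnostic accuracy, so each patient and lesion needs a truth status that does not come from the index test. For one admitted class of patients, 5.4 does not clearly supply it. Three paths fall outside both tiers when there is no earlier specimen:
- the patient is only observed;
- the work-up is negative and no therapy is given;
- tissue is first obtained by biopsy or surgery after the study PET.

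The third path would yield the most direct evidence on a PET focus.

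If the chance of acquiring a reference is related to the PET result, accuracy among verified cases is biased (partial verification). The background makes such a relation plausible. Section 2.0 says imaging can guide therapy and that receptor status must be confirmed before receptor-targeted radionuclide therapy, which is a nonsurgical therapy. In Section 2.3, one cited study of a sister tracer reports changed management in 36 patients (70.6%), who were then deemed suitable for that therapy. Another reports high management impact in 47%, including direction to curative surgery or to systemic therapy. The systemic route can lead to a tier 2 reference; the surgical route may not.

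**Working it through.** **1. The plan's own precision.** The inputs are 40 patients and 80 lesions, 60% of them positive, so 48 positive and 32 negative (5.4, Justification of Sample Size). The worst-case Wald half-width is 1.96 × √(0.25/n):
- n = 48: 14.1% (stated 14%)
- n = 32: 17.3% (stated 17%)
- n = 40: 15.5% (stated 15%)

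The stated figures reproduce, but only with a reference for all 80 lesions and all 40 patients (and with lesions treated as independent).

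**2. Loss of precision.** Suppose a share f has no reference, unrelated to PET, so that n becomes n(1 − f). The values of f are assumptions.

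| f | Lesion sensitivity | Lesion specificity | Patient sensitivity |
|---|---|---|---|
| 10% | 14.9% | 18.3% | 16.3% |
| 20% | 15.8% | 19.4% | 17.3% |
| 50% | 20.0% | 24.5% | 21.9% |

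**3. Bias among patients without histology, if verification is related to PET.** Let v1 and v0 be the verified shares of PET-positive and PET-negative NET cases. Apparent sensitivity = Se·v1 / [Se·v1 + (1 − Se)·v0]. The documents give neither v1 nor v0, so both are assumed.

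| True Se | v1 = 0.9, v0 = 0.4 | v1 = 0.9, v0 = 0.6 |
|---|---|---|
| 80% | 0.72/0.80 = 90% | 0.72/0.84 = 86% |
| 85% | 0.765/0.825 = 93% | 0.765/0.855 = 90% |
| 90% | 0.81/0.85 = 95% | 0.81/0.87 = 93% |

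The rise is about 3 to 10 points. With v1 = v0 it is zero.

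**4. The same bias over the whole trial.** Let a share s lack histology and all others be verified. Then TP ∝ Se(1 − s + s·v1) and FN ∝ (1 − Se)(1 − s + s·v0).
- s = 25%, Se 80%, v0 0.4: 0.780/(0.780 + 0.170) = 82.1%, up 2.1 points
- s = 25%, Se 90%, v0 0.6: 0.8775/(0.8775 + 0.090) = 90.7%, up 0.7
- s = 50%, Se 80%, v0 0.4: 0.760/(0.760 + 0.140) = 84.4%, up 4.4
- s = 50%, Se 90%, v0 0.6: 0.855/(0.855 + 0.080) = 91.4%, up 1.4

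**5. Lesion-level specificity moves the other way.** Assume sensitivity and specificity both 0.80, all PET-positive and half of PET-negative lesions verified. Sensitivity appears as 38.4/(38.4 + 4.8) = 0.889 and specificity as 12.8/(12.8 + 6.4) = 0.667.

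**6. The opposite direction at patient level.** If every patient is counted as having NET, a suspected patient without NET and with a negative PET becomes a miss. The cited 84-patient study of this tracer (2.3, item 3) had 69 TP, 2 FN, 12 TN and 1 FP. Its sensitivity was 69/71 = 97%. Counting all 84 as diseased would give 70/84 = 83%. This is an illustration only; that study's mix of patients need not match this trial's.

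**7. The 5.2 PET-only rule.** With 0.80/0.80 and 48/32 lesions, there are 6.4 false positives. If all lack a CT/MRI correlate and are relabelled NET, sensitivity becomes 44.8/54.4 = 0.82 and specificity 25.6/25.6 = 1.00.

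**The case against.** The best defence is that 5.2 promises CT/MRI confirmation in all patients, 3.6 guarantees a baseline scan and 5.1.3 adds a comparison with prior imaging, so nobody is without a reference. This does not close the gap. Tier 2 of 5.4 asks for initial and follow-up imaging, 5.2 sets no date, and if baseline CT were the truth it would also be a comparator in the McNemar test.

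Other parts of the defence stand, and they limit the point:
- A reader might infer that many patients lack a reference. The documents give no share without histology or without nonsurgical therapy.
- A reader might infer that the plan makes verification depend on the PET result. Section 5.4 contains no such rule, and earlier pathology predates the PET. The relation is an inference from the background. The explicit PET dependence is in 5.2, and that is incorporation of the index test into the truth, a different problem.
- A reader might set the 3 to 10 points against the patient-level ±15%. Those points apply only to patients without histology; the whole-trial effect is smaller. The ±15% also comes from all 40 patients, which fits counting everyone as diseased, and then the error could run downward.
- A reader might conclude that post-PET pathology is discarded, or that no later imaging is foreseen. The word *previous* may qualify only the biopsy, and tier 2 applies in the absence of pathology reports generally. Tier 2 also names follow-up imaging; what is missing is a window and a way to collect it.

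**Conclusion.** The concern holds in limited form. On a literal reading of 5.4, patients without earlier tissue who receive no nonsurgical therapy, or whose tissue is first obtained after the study PET, have no defined reference standard. There is no rule for unverified cases. This matters because accuracy is the primary objective.

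The size cannot be fixed from the documents. On the assumed verification rates and true sensitivities of 80-90%, the upward bias is 3 to 10 points among patients without histology and 0.7 to 4.4 points overall if 25-50% lack it. It vanishes if verification is equal, and the patient-level error could be downward if everyone is counted as having NET. Whatever the direction, the stated precision presumes complete verification. The documents do not support a claim that PET-dependent verification is built into the plan, or that the trial's sensitivity will be inflated by a known amount.

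**What to change.** In 5.4 (Statistical Analysis):
1. Accept pathology obtained before or after the study PET, matched to the lesion or site.
2. Where there is none, use initial plus routine-care follow-up CT/MRI, whether or not therapy was given, abstracted from the chart to a fixed cut-off date for every patient and judged without reference to the PET result.
3. State that the 5.2 rule for PET-only foci does not define truth.
4. Report patients and lesions still without a reference as unverified, split by PET result, and give accuracy with them counted all as NET and all as not NET.

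The cost is wording, some chart abstraction and a later final analysis; no added scan or biopsy is needed. Routine care will still influence who gets verified, so the bounds show residual verification bias but do not remove it.

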1.0 Objectives

1.1 Main objective:

The primary goal of the analysis is to estimate the diagnostic accuracy of 68Ga-DOTATOC PET-CT for detecting NET compared to conventional imaging techniques.

1.2 Secondary objectives:

We will assess the safety and tolerability of 68Ga-DOTATOC PET-CT by measuring the number of adverse events in patients receiving 68Ga-DOTATOC PET-CT.

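### Section 5.4 compares modalities by kappa and McNemar's test only, and plans no paired difference with a confidence interval for a comparative estimation objective

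*Combined protocol and SAP*

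**What the plan says.** Section 1.1 sets the aim to "estimate the diagnostic accuracy of 68Ga-DOTATOC PET-CT for detecting NET compared to conventional imaging techniques". Section 5.0 and the opening of section 5.4 (Statistical Analysis) repeat it.

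On estimation, section 5.4 says: "We will compute the relevant proportions and corresponding 95% confidence intervals, with adjustment for correlated data from the same patient". It does not say whether these proportions are for PET-CT alone or for every modality.

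On comparison, it says: "Kappa statistics will be computed and McNemar's test will be performed to compare the sensitivity and specificity". The tests compared are "PET-CT with SPECT and diagnostic CT for detecting NET", and "p-values < 0.05 will be considered statistically significant". No difference, ratio, or interval for either is named. Kappa is given no stated target: it could be between modalities, against the reference, or between readers.

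For the patient-level analysis: "Since all patients are expected to have at least one NET lesion, only sensitivity can be estimated in the analysis by patient".

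Two other places matter. Section 5.2 says that each PET scan "will be read by two independent, board certified nuclear medicine physicians blinded to the results of other scan", and that In-111 octreotide images are compared only where they exist. The sample size section finds it "feasible to recruit a total of 40 patients", expects 80 lesions of which 60% are positive, and gives precision for PET-CT alone: ±14% and ±17% for lesion sensitivity and specificity, and ±15% for patient sensitivity.

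**The concern.** A comparative estimation objective needs an estimated contrast and its uncertainty. McNemar's test asks whether the two discordant counts differ; it does not say by how much the sensitivities differ. Kappa measures agreement between two classifications, and good or poor agreement does not say which test is better. If every modality gets its own proportion and interval, a reader can subtract the proportions, but two separate intervals ignore that the same patients had both tests.

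Clustering is a second gap. The adjustment for several lesions per patient is attached to the intervals for the proportions. Nothing extends it to McNemar's test, although section 5.4 plans lesion-level analyses.

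At stake is whether the report can state how many percentage points PET-CT gains or loses against each comparator, and with what uncertainty.

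**Working it through.** **Inputs.** From the sample size section: 40 patients, 80 lesions, 60% positive, so 48 positive and 32 negative. From the 84-patient DOTATOC study summarised in section 2.3: 71 diseased patients, PET positive in 69, SPECT positive in 37, and 32 discordant patients, all PET positive and SPECT negative. For PET v CT in that study: 67 diseased by the CT counts, with 26 missed by CT only and 2 by PET only. Tables are written (both positive, first only, second only, neither).

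**1. The plan's own precision.** Half-width = 1.96 × √(0.25/n): 14.1% for n = 48, 17.3% for n = 32 and 15.5% (15.495) for n = 40. These match the stated ±14%, ±17% and ±15%. They apply to one test, with no allowance for clustering, and not to a difference.

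**2. McNemar gives no size.** For discordant counts 10 and 2, exact p = 2 × (1 + 12 + 66)/2^12 = 158/4096 = 0.039, whatever the n. With b and c the discordant counts, d = (b - c)/n and SE = √(b + c - (b - c)²/n)/n:
- n = 20: d = 8/20 = +40 points, SE = √8.8/20 = 0.148, 95% CI +11 to +69.
- n = 71: d = 8/71 = +11 points, SE = √11.10/71 = 0.047, 95% CI +2 to +20.

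**3. Kappa has no direction.** Kappa = (po - pe)/(1 - pe). For (28, 18, 0, 2), n = 48: po = 30/48 = 0.625, pe = (46×28 + 2×20)/48² = 0.576, kappa = 0.115, d = +37.5 points. For the mirror image (28, 0, 18, 2), kappa is again 0.115 and d = -37.5 points.

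**4. Kappa against the reference when all patients have disease.** If k of 40 are detected, po = k/40 and pe = (k×40)/40² = k/40. Kappa is therefore 0 for k = 20, 30 or 39, and 0/0 for k = 40.

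**5. What the missing estimate looks like.** The cited PET v SPECT table among the diseased is (37, 32, 0, 2). d = 32/71 = +45.1 points, SE = √(32 - 32²/71)/71 = 0.0590, 95% CI 33.5 to 56.6. Exact p = 2 × 0.5^32 = 5 × 10^-10, and kappa = 0.061. Neither of the last two conveys the first. Treating the two proportions as independent gives SE = √[(69×2 + 37×34)/71²/71] = 0.0625, a half-width of 12.2 points against 11.6 paired. Ignoring the pairing costs little here; the amount depends on how results co-vary.

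**6. Precision to expect for sensitivity.** Half-width = 1.96 × √[(q - d²)/n], with q the discordant share. The values of q and d are assumptions from the cited study.
- PET v SPECT (q = 0.45, d = 0.45): ±14.1 points with 48 lesions, ±15.4 with 40 patients.
- PET v CT (q = 28/67, d = 24/67): ±15.2 and ±16.7.
- Clustering: the documents give no design effect. At 1.5, the lesion figures become 14.1 × √1.5 = 17.2 and 15.2 × √1.5 = 18.6. Since 48 positive lesions over 40 patients is only 1.2 each on average, 1.5 needs strong correlation and uneven lesion counts, so the range 1 to 1.5 is an assumption.
- SPECT subset: the share is not given. If half the patients had it (assumed), the patient-level figure is 15.4 × √2 = ±21.8.

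**7. Lesion specificity, n = 32.** Assuming equal specificities and discordance of 10% to 20%: ±11.0 to ±15.5 points, or ±13.4 to ±19.0 at a design effect of 1.5. At equal discordance and difference this is √(48/32) = 1.22 times as wide as for sensitivity.

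**8. Unadjusted lesion-level McNemar.** A design effect of 1.3 to 1.5 would mean a standard error understated by a factor of √1.3 = 1.14 to √1.5 = 1.22. With little clustering the effect is small.

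**The case against.** The strongest defence is that the planned proportions are not limited to PET-CT. Read with the comparative objective, they can cover SPECT and CT, and a point difference then follows. McNemar's test is a correct paired test at patient level. The kappa sentence has two clauses, and the words about comparing can attach to McNemar alone; kappa may even be meant for the two PET readers. On this view the gap is one of reporting.

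Much of that stands, and it rules out three stronger readings.

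- A reader might infer that the objective gets no comparative estimate at all. The text does not support this, because separate proportions may allow one by subtraction.
- A reader might infer that kappa will rank the tests wrongly. There are no trial data yet, and the plan does not say that it ranks tests by kappa. In the cited study, between-test kappa among the diseased is 0.061 for PET-SPECT and -0.059 for PET-CT, although the sensitivity gap is larger for SPECT (45.1 v 35.8 points). However, the bootstrap intervals touch (0.00 to 0.16 and -0.14 to 0.00). Kappa against the reference puts PET first (0.868) and ties SPECT and CT (both 0.218). For the 19-patient study in section 2.0, at 60% prevalence, kappa is 0.925, 0.684 and 0.537 for Ga-68 DOTATATE, MRI and Tc-99m octreotide, the same order as accuracy.
- A reader might infer that almost no lesion is negative on both tests, because foci are listed from scans. The plan projects 40% of lesions as negative, pathology or follow-up can add lesions that both tests missed, and a lesion seen only on CT is negative on both PET and SPECT.

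What the defence does not supply is an interval for the difference, a clustered lesion-level test, or a stated purpose for kappa.

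**Conclusion.** The point holds in this form: for a comparative estimation objective, the plan names no paired difference with a confidence interval. McNemar's p-value and kappa cannot stand in for one, and the stated clustering adjustment does not reach the lesion-level test. Steps 2 to 4 are exact arithmetic and need no assumption about the trial. The precision figures rest on discordance taken from one cited study, or assumed for specificity, and on an assumed design effect of 1 to 1.5. The CT figures are the less secure, since the CT counts imply 67 diseased patients against 71 for PET and SPECT.

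This should be corrected before analysis. It concerns how the comparison is summarised and does not invalidate the design or the patient-level McNemar test.

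**What to change.** In section 5.4 (Statistical Analysis), for each comparator:

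- Define the analysis set as patients or lesions with both tests and state its n, particularly for SPECT.
- Report each modality's sensitivity and lesion specificity, and the paired difference with a 95% interval. Use a score or Newcombe paired interval by patient, and a patient-clustered interval (GEE or cluster bootstrap) by lesion.
- Show the paired 2×2 tables.
- Keep McNemar's test as a supporting p-value, in a clustered version at lesion level.
- Do not use kappa to compare sensitivity or specificity. State its agreement purpose, for example between the two independent PET reads already collected.

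No new data are needed. The cost is some plan wording and SAS programming, and difference intervals whose width will be plain to see, especially for specificity and for SPECT if few patients have it.
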